9.3 POPULATIONS FOR ANALYSES

- Modified Intention-to-Treat Analysis Dataset: participants who are enrolled for at least 7 days of the 90-day intervention period
- Per-Protocol Analysis Dataset: participants who complete the 90-day intervention period and post-study interview and questionnaire.

9.4 STATISTICAL ANALYSES

9.4.1 GENERAL APPROACH

Categorical and continuous data will be presented as percentages, means with standard deviations, median, range.

9.4.2 ANALYSIS OF THE PRIMARY EFFICACY ENDPOINT(S)

Given the small sample size and specification of secondary endpoints, descriptive statistics are sufficient to either accept or reject the null hypothesis.

9.4.3 ANALYSIS OF THE SECONDARY ENDPOINT(S)

Given the small sample size and specification of all secondary endpoints, descriptive statistics are sufficient to either accept or reject the null hypotheses.

9.4.4 SAFETY ANALYSES

Not applicable.

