2.3 RISK/BENEFIT ASSESSMENT

2.3.1 KNOWN POTENTIAL RISKS

A potential risk to participants is breach of confidentiality, which exists both as an immediate and long-term risk. There is also an immediate risk that the platform hardware or software may malfunction in some way, which may affect data capture, data transmission, or medication dispensing. These errors may affect the reliability of the device in providing timely dosage reminders, accurate remote monitoring, and accurate dispensing of medication.

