8.2 SAFETY AND OTHER ASSESSMENTS

Automated medication logs from the HiDO device, and manual audits thereof, will be used to assess safety – for instance, in the unlikely event that the HiDO device contributes to substantially lower medication adherence as compared to baseline. Logs will be audited monthly beginning in Week 4 of the earliest participant enrollment.

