8.3.3.2 RELATIONSHIP TO STUDY INTERVENTION

All adverse events (AEs) must have their relationship to study intervention assessed by the clinician who examines and evaluates the participant based on temporal relationship and his/her clinical judgment. The degree of certainty about causality will be graded using the categories below. In a clinical trial, the study product must always be suspect.

- **Related** – The AE is known to occur with the study intervention, there is a reasonable possibility that the study intervention caused the AE, or there is a temporal relationship between the study intervention and event. Reasonable possibility means that there is evidence to suggest a causal relationship between the study intervention and the AE.
- **Not Related** – There is not a reasonable possibility that the administration of the study intervention caused the event, there is no temporal relationship between the study intervention and event onset, or an alternate etiology has been established.

OR

- **Definitely Related** – There is clear evidence to suggest a causal relationship, and other possible contributing factors can be ruled out. The clinical event, including an abnormal laboratory test result, occurs in a plausible time relationship to study intervention administration and cannot be explained by concurrent disease or other drugs or chemicals. The response to withdrawal of the study intervention (dechallenge) should be clinically plausible. The event must be pharmacologically or phenomenologically definitive, with use of a satisfactory rechallenge procedure if necessary.
- **Probably Related** – There is evidence to suggest a causal relationship, and the influence of other factors is unlikely. The clinical event, including an abnormal laboratory test result, occurs within a reasonable time after administration of the study intervention, is unlikely to be attributed to concurrent disease or other drugs or chemicals, and follows a clinically reasonable response on withdrawal (dechallenge). Rechallenge information is not required to fulfill this definition.
- **Potentially Related** – There is some evidence to suggest a causal relationship (e.g., the event occurred within a reasonable time after administration of the trial medication). However, other factors may have contributed to the event (e.g., the participant's clinical condition, other

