8.3.4 TIME PERIOD AND FREQUENCY FOR EVENT ASSESSMENT AND FOLLOW-UP

The occurrence of an adverse event (AE) or serious adverse event (SAE) may come to the attention of study personnel during study visits and interviews of a study participant presenting for medical care, or upon review by a study monitor.

All AEs including local and systemic reactions not meeting the criteria for SAEs will be captured on the appropriate case report form (CRF). Information to be collected includes event description, time of onset, clinician’s assessment of severity, relationship to study product (assessed only by those with the training and authority to make a diagnosis), and time of resolution/stabilization of the event. All AEs occurring while on study must be documented appropriately regardless of relationship. All AEs will be followed to adequate resolution.

Any medical condition that is present at the time that the participant is screened will be considered as baseline and not reported as an AE. However, if the study participant’s condition deteriorates at any time during the study, it will be recorded as an AE.

Changes in the severity of an AE will be documented to allow an assessment of the duration of the event at each level of severity to be performed. AEs characterized as intermittent require documentation of onset and duration of each episode.

The Principal Investigator will record all reportable events with start dates occurring any time after informed consent is obtained until 7 (for non-serious AEs) or 30 days (for SAEs) after the last day of study participation. At each study visit, the investigator will inquire about the occurrence of AE/SAEs since the last visit. Events will be followed for outcome information until resolution or stabilization.

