8.3.5 ADVERSE EVENT REPORTING

Serious adverse events will be collected throughout the study period. All serious adverse events must be reported to HiDO Technologies within 24 hours of discovery or notification of the event. Initial serious adverse event information and all amendments or additions must be recorded on a Serious Adverse Event Report Form and submitted to HiDO Technologies. The Principal Investigator will notify the IRB of serious adverse events within seven days or as otherwise specified by local policies.

Disease-related events (DREs) can be expected to occur among the study population, which may include HIV/AIDS patients. These events are recorded by research staff, but are not reported as for AEs.

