10.1.9 DATA HANDLING AND RECORD KEEPING

10.1.9.1 DATA COLLECTION AND MANAGEMENT RESPONSIBILITIES

Data collection is the responsibility of the investigator. The investigator is responsible for ensuring the accuracy, completeness, legibility, and timeliness of the data reported.

Hardcopies of the study visit worksheets will be provided for use as source document worksheets for recording data for each participant enrolled in the study. Data recorded in the electronic case report form (eCRF) derived from source documents should be consistent with the data recorded on the source documents.

Study data (including adverse events (AEs), concomitant medications, and expected adverse reactions data) are stored on AWS, a 21 CFR Part 11-compliant cloud computing platform. The data system includes password protection; internal quality checks are conducted manually to identify data that appear inconsistent, incomplete, or inaccurate. Study data will be entered directly from the source documents.

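### Section 9.4.4 rules out safety analyses although AEs and SAEs are collected and section 8.2 promises a safety assessment, so no safety summary or safety denominator is prespecified

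*Combined protocol and SAP*

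**What the plan says.** Section 9.4.4, headed "9.4.4 SAFETY ANALYSES", states that the item is not applicable and says nothing more. Other sections of the same document commit the trial to safety data:

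- Section 8.2: device logs and manual audits of them "will be used to assess safety". The example given is adherence substantially below baseline. No threshold, comparison or method follows.
- Sections 8.3.3.1 and 8.3.3.2: each AE receives a CTCAE grade and a causality category. "The degree of certainty about causality will be graded using the categories below", and the categories are two alternative scales joined by OR.
- Section 8.3.4: AEs go on a case report form, with events recorded from consent "until 7 (for non-serious AEs) or 30 days (for SAEs) after the last day of study participation".
- Section 8.3.5: "Serious adverse events will be collected throughout the study period".
- Section 10.1.9.1: "Study data (including adverse events (AEs), concomitant medications, and expected adverse reactions data) are stored on AWS".
- Section 2.3.1: hardware or software malfunction is an immediate risk, "which may affect data capture, data transmission, or medication dispensing".

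Section 9.3 defines two analysis sets: a modified intention-to-treat set (at least 7 days enrolled in the intervention period) and a per-protocol set (completers). It defines no safety set.

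**The concern.** An analysis section cannot sensibly be inapplicable when the protocol requires its inputs to be collected and promises the assessment elsewhere. This is an explicit entry, not a missing detail, so an analyst who follows it produces no safety table.

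If a table were produced anyway, three choices would be made after the data were seen: who is in the denominator, which relatedness scale defines a device-related event, and what adherence below baseline is measured against. In a study of about 24 people each choice can visibly move the result.

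**Working it through.** The documents give no safety figure to reproduce. The one number needed is how many people receive the device. Section 9.2 targets 24, aiming at 15 or more completers at 60% completion: 15 / 0.60 = 25 against 24 stated (24 × 0.60 = 14.4). That is close enough to use 24 here.

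**1. Denominator.** Someone who leaves the study on day 3 has fewer than 7 days enrolled, so is outside the modified intention-to-treat set, and has not completed 90 days, so is outside the per-protocol set. Section 8.3.4 still collects that person's events. Section 7.1 separates stopping the device from leaving the study, so the gap concerns those who leave the study. Their number cannot be known in advance.

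**2. Whether the sample is too small to analyse.** Exact limits for the proportion of participants affected, n = 24:
- 0 of 24, two-sided 95% upper limit: 1 − 0.025^(1/24) = 14.2%.
- 0 of 24, one-sided 95% upper limit: 1 − 0.05^(1/24) = 11.7%.
- 1 of 24, Clopper-Pearson 95% interval: 0.1% to 21.1%.

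The chance of seeing at least one affected participant is 1 − (1 − p)^24. The documents give no event rate, so p is an assumption:

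| Assumed true risk p | Chance of at least one affected |
|---|---|
| 1% | 21% |
| 5% | 71% |
| 10% | 92% |
| 20% | 99.5% |

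At an assumed 5% risk, a clean result would still occur with probability 100% − 71% = 29%. The intervals are wide but computable, and they show what a zero count means.

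**3. Relatedness.** On the two-level scale in section 8.3.3.2, a temporal relationship is enough for an event to be called related. The five-level scale looks for evidence of causation and weighs other causes, so the same event may be only potentially related. A count of device-related AEs thus depends on a choice not yet made.

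**4. Adherence against baseline.** Under the schedule of activities, baseline adherence is self-reported, while adherence during the intervention comes from the device. Setting one against the other mixes two measures. Section 4.1 lists a self-assessment questionnaire both before and after the intervention, which allows a like-for-like comparison.

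**5. Device faults.** Section 2.3.1 names the risk, but no section sets up a malfunction log, case report form item or endpoint. The nearest items are the usability error counts in section 3, which are not said to include device faults, and the event-driven form for unanticipated adverse device effects in section 8.3.6.

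**The case against.** The best defence is that this is a descriptive pilot with no safety objective or endpoint in section 3. Section 9.4.1 already presents categorical data as percentages and section 9.4.8 tabulates individual data. Events also reach the sponsor and the IRB under sections 8.3.5, 8.3.6 and 8.4.2. Section 8.2 can be read as surveillance during the study, since it speaks of monthly audits, and not as a promise of an end-of-study analysis.

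Part of this stands. A reader might infer from section 9.4.4 that the trial cannot report safety. The documents do not support that: the data are held and the general text permits description. Exact intervals are also partly a preference, because counts and percentages alone would remove the inconsistency.

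The rest does not answer the point. Sections 9.4.1 and 9.4.8 name no safety variable or denominator, while the entry specific to safety rules the analysis out. Case-by-case reporting is not a summary. Even read as surveillance, section 8.2 describes an assessment whose comparison is undefined.

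**Conclusion.** The point holds as an inconsistency with a practical result: safety data are collected and a safety assessment is promised, but no summary or denominator is prespecified, and those who leave the study within 7 days are in no analysis set. It should be corrected. The 14.2% limit assumes that 24 people receive the device and none is affected. Section 7.2 allows replacement, so the number could differ.

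Several stronger readings should be resisted:

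- A reader might infer that device malfunctions are already collected. They are named as a risk only; the lack of specified capture is a separate gap.
- A reader might quote the zero-event limit for 15 completers, 1 − 0.025^(1/15) = 21.8%. Safety belongs to everyone who received the device, so that is the wrong denominator.
- A reader might infer that an absence of events would be presented as proof of safety in a first study. Section 4.2 makes its readiness statement conditional, ties it to usability and preliminary adherence, and mentions earlier informal user testing.
- A reader might infer that relatedness cannot be summarised at all. The five-level scale could be collapsed to two; what is missing is the choice.
- Safety oversight is also marked as not applicable in section 10.1.6, but that is governance and adds nothing to the analysis point.

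**What to change.** Replace the entry in section 9.4.4 with a descriptive analysis:

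1. Population: all participants who received the device, whatever their time on study, added to section 9.3 as the safety set.
2. Number and percent with any AE, any SAE and any device-related AE, by grade and by relatedness, with exact 95% intervals for the participant-level proportions. Keep one of the two scales in section 8.3.3.2 and delete the other.
3. A descriptive comparison of adherence with baseline, to match section 8.2, using the pre- and post-study self-assessments. The schedule of activities, as it reads here, shows the self-report only at screening and should be brought into line with section 4.1.
4. Dispensing faults and outages per participant and per 100 scheduled doses, only if the device logs already record them. If they do not, capture must be specified first, which is a separate change.

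Items 1 and 2 use data already collected. The cost is one or two extra tables with no change in sample size. The drawback is that the published intervals will be wide.

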9.4.5 BASELINE DESCRIPTIVE STATISTICS

For each part of the study, descriptive statistics (N, mean, SD, median, minimum, and maximum) will be generated for continuous demographic variables and pre-intervention medication adherence variables.

Demographic variables of screen failure participants and reasons for screen failures will be summarized overall for participants who are screened, but not enrolled in the study. Individual demographic characteristics, date of informed consent, and reason for screen failure will be listed.

9.4.6 PLANNED INTERIM ANALYSES

Not applicable.

9.4.7 SUB-GROUP ANALYSES

The sample size is not sufficient to conduct formal sub-group analyses, and the study was not designed for this purpose.

9.4.8 TABULATION OF INDIVIDUAL PARTICIPANT DATA

Individual participant data will be tabulated by measure and time point.

9.4.9 EXPLORATORY ANALYSES

Qualitative data produced by answers to open-ended interview questions will be reviewed to determine any relevant aspects of the participant's experience with the device that were not captured by the System Usability Scale or the Net Promoter Scale.

10 SUPPORTING DOCUMENTATION AND OPERATIONAL CONSIDERATIONS

10.1 REGULATORY, ETHICAL, AND STUDY OVERSIGHT CONSIDERATIONS

10.1.1 INFORMED CONSENT PROCESS

10.1.1.1 CONSENT/ASSENT AND OTHER INFORMATIONAL DOCUMENTS PROVIDED TO PARTICIPANTS

Consent forms describing in detail the study intervention, study procedures, and risks are given to the participant and written documentation of informed consent is required prior to starting intervention/administering study intervention. The following consent materials are submitted with this protocol:

- Recruitment flyer
- Device flyer
- Consent form
- Informed consent SOP²

10.1.1.2 CONSENT PROCEDURES AND DOCUMENTATION

Informed consent is a process that is initiated prior to the individual's agreeing to participate in the study and continues throughout the individual's study participation. Consent forms will be Institutional Review Board (IRB)-approved and the participant will be asked to read and review the document. The investigator will explain the research study to the participant and answer any questions that may arise. A verbal explanation will be provided in terms suited to the participant's comprehension of the purposes, procedures, and potential risks of the study and of their rights as research participants. Participants will have the opportunity to carefully review the written consent form and ask questions prior to signing. The participants should have the opportunity to discuss the study with their family or surrogates or think about it prior to agreeing to participate. The participant will sign the informed consent document prior to any procedures being done specifically for the study. Participants will be informed that participation is voluntary and that they may withdraw from the study at any time, without prejudice. A copy of the informed consent document will be given to the participants for their records. The informed consent process will be conducted and documented in the source document (including the date), and the form signed, before the participant undergoes any study-specific interventions. The rights and welfare of the participants will be protected by emphasizing to them that the quality of their medical care will not be adversely affected if they decline to participate in this study.

10.1.2 STUDY DISCONTINUATION AND CLOSURE

This study may be temporarily suspended or prematurely terminated if there is sufficient reasonable cause. Written notification, documenting the reason for study suspension or termination, will be provided by the suspending or terminating party to study participants, investigators, funding agencies, and regulatory authorities. If the study is prematurely terminated or suspended, the Principal Investigator (PI) will promptly inform study participants, the Institutional Review Board (IRB), and sponsor and will provide the reason(s) for the termination or suspension. Study participants will be contacted, as applicable, and be informed of changes to study visit schedule.

Circumstances that may warrant termination or suspension include, but are not limited to:

- Determination of unexpected, significant, or unacceptable risk to participants

² This document describes the steps of the consent process; it is not provided to participants.

- Demonstration of efficacy that would warrant stopping
- Insufficient compliance to protocol requirements
- Data that are not sufficiently complete and/or evaluable
- Determination that the primary endpoint has been met
- Determination of futility

Study may resume once concerns about safety, protocol compliance, and data quality are addressed, and satisfy the sponsor, IRB and/or Food and Drug Administration (FDA).

10.1.3 CONFIDENTIALITY AND PRIVACY

Participant confidentiality and privacy is strictly held in trust by the participating investigators, their staff, and the sponsor(s) and their interventions. This confidentiality is extended to cover testing of biological samples and genetic tests in addition to the clinical information relating to participants. Therefore, the study protocol, documentation, data, and all other information generated will be held in strict confidence. No information concerning the study or the data will be released to any unauthorized third party without prior written approval of the sponsor.

All research activities will be conducted in as private a setting as possible.

The study monitor, other authorized representatives of the sponsor, representatives of the Institutional Review Board (IRB), regulatory agencies or pharmaceutical company supplying study product may inspect all documents and records required to be maintained by the investigator. The study site will permit access to such records.

The study participant's contact information will be securely stored at the research site for internal use during the study. At the end of the study, all records will continue to be kept in a secure location for as long a period as dictated by the reviewing IRB, Institutional policies, or sponsor requirements.

Study participant research data, which is for purposes of statistical analysis and scientific reporting, will be transmitted to and stored at HiDO Technologies. This will not include the participant's contact or identifying information. Rather, individual participants and their research data will be identified by a unique study identification number. The study data entry and study management systems used by clinical sites and by HiDO Technologies research staff will be secured and password protected. At the end of the study, all study databases will be de-identified and archived at HiDO Technologies.

10.1.4 FUTURE USE OF STORED SPECIMENS AND DATA

Not applicable.

10.1.6 SAFETY OVERSIGHT

Not applicable.

10.1.7 CLINICAL MONITORING

Not applicable.

10.1.8 QUALITY ASSURANCE AND QUALITY CONTROL

The clinical site will perform internal quality management of study conduct, data collection, documentation, and completion. An individualized quality management plan will be developed to describe a site's quality management.

Quality control (QC) procedures will be implemented beginning with the data entry system and data QC checks that will be run on the database will be generated. Any missing data or data anomalies will be flagged for clarification/resolution.

The investigational site will provide direct access to all trial related sites, source data/documents, and reports for the purpose of monitoring and auditing by the sponsor, and inspection by local and regulatory authorities.

10.1.9 DATA HANDLING AND RECORD KEEPING

10.1.9.1 DATA COLLECTION AND MANAGEMENT RESPONSIBILITIES

Data collection is the responsibility of the investigator. The investigator is responsible for ensuring the accuracy, completeness, legibility, and timeliness of the data reported.

Hardcopies of the study visit worksheets will be provided for use as source document worksheets for recording data for each participant enrolled in the study. Data recorded in the electronic case report form (eCRF) derived from source documents should be consistent with the data recorded on the source documents.

Study data (including adverse events (AEs), concomitant medications, and expected adverse reactions data) are stored on AWS, a 21 CFR Part 11-compliant cloud computing platform. The data system includes password protection; internal quality checks are conducted manually to identify data that appear inconsistent, incomplete, or inaccurate. Study data will be entered directly from the source documents.

